Screening/Assessment: A quick screen will be used to initially determine study eligibility. This questionnaire is focused on inclusion/exclusion of psychiatric diagnoses, medical status, and ability and willingness to complete study procedures. Potential subjects will be given a full description of the study procedures and asked to read and sign an IRB-approved Informed Consent Form if interested in participating. Appropriate modules of the Mini-International Neuropsychiatric Interview (M.I.N.I.) will be used to assess exclusionary psychiatric diagnoses (Sheehan et al, 1998). A general medical history and physical exam will also be performed to ensure that the subject is eligible to participate. Urine drug screens will be performed at the screening visit in order to rule out substance abuse. For female participants, a urine pregnancy test will be completed prior to urine drug screening.

Group Assignment/Intervention: After inclusion into the study, participants will be randomized into one of two intervention groups. Group 1 (n=20) will receive a standard capsule containing 50mg of riboflavin to be ingested once daily and dispensed with a MEMS 6 TrackCap. Group 2 (n=20) will receive an ID-CAP-M containing 50mg of riboflavin to be ingested once daily. Their compliance will be measured by data collected by an e-Tect reader worn around the neck on a lanyard. Participants randomized to this group will also receive reminder calls and/or text messages to ingest the study medication if a signal is not sent from the e-Tect reader to the study team within one hour of the end of the scheduled medication administration time window. In the event that a daily pill detection is not obtained for a subject in Group 2, but they report taking the pill as directed, they will be asked to come in to the clinic to provide a urine sample for riboflavin assessment. Group 2 participants will be provided with a loaner smartphone for e-Tect application download if they do not own a personal one or do not wish to use their own. The smartphones will be activated by a data plan, and will be of no cost to the participants. All applications of the phone will be disabled with the exception of the e-Tect

Program Director/Principal Investigator (Last, First, Middle): [name]

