software needed to transfer data. Providing the necessary technology will prevent the exclusion of individuals without smartphone access or those who cannot afford to pay for a smartphone data plan. Group 2 will also provide biometric data for compliance measurement, specifically ECG. These measurements will be collected by their eTect reader.

Study visits: The study duration will be approximately six weeks. At the initial randomization visit, participants will be trained on use of the devices (MEMS 6 TrackCap for Group 1 and biometric data collection/ID-Cap-M for Group 2) and medication administration will be observed. A 30-day supply of study capsules will be dispensed. Participants will be instructed to take each dose by 12PM daily. Participants will return to the clinic approximately five weeks (within one week following last dose) after their initial randomization for an End of Study (EOS) visit to discuss overall medication compliance and return their study equipment (pill bottles, unused capsules if any, and MEMS 6 TrackCap or ID Cap Reader). For those in Group 2, passage of ID-Caps will be confirmed at this visit via abdominal x-ray.

Safety Assessment: Adverse events (AEs) will be assessed at the End of Study visit. The research clinician will identify potential adverse events by asking the subject a question such as: "Have you had any problems or side effects since we saw you last (such as flu, headache, nausea, or other problems)?" The type of AE, severity of AE, and relationship to the study intervention will be recorded. At their initial randomization visit, subjects will be given detailed information regarding clinic contact procedures during and afterhours should this be necessary during their study participation. An abdominal X-ray will also be completed at study completion to verify passage of the capsules from the gastrointestinal tract for those in Group 2.

Follow-up Plan: In the event that an adverse event occurs during the study, a subject will be followed to resolution. Participants will be provided incentive compensation to attend the EOS visit and return the MEMS 6 TrackCap or e-Tect reader and cell phone (if one was provided).

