1. RISKS TO THE SUBJECTS

a. Human Subjects Involvement and Characteristics

Admission into the study is open to men, women, and children 18 to 65 years of age, and to all racial and ethnic groups. We anticipate we will screen (by telephone or in person) about 60 potential subjects. A total of 40 healthy men and women will be enrolled. We will recruit subjects from multiple

Program Director/Principal Investigator (Last, First, Middle): [name]

sources, primarily through advertising in local media via television, newspaper, and word of mouth among subjects.

Inclusion Criteria

- Must be between the ages of 18 and 65 years.
- If female and of childbearing potential, must agree to use acceptable methods of birth control for the duration of the trial.
- Must consent to random assignment, and be willing to commit to capsule ingestion.
- Must be able to read and provide informed consent.
- Must function at an intellectual level sufficient to allow accurate completion of assessments.
- Must have a Body Mass Index (BMI) below 35.

Exclusion Criteria

- Women who are pregnant, nursing, or plan to become pregnant during the course of the study.
- Must not have evidence of a significant medical condition which may affect capsule passage through the gastrointestinal tract (including, but not limited to, Crohn's disease, small bowel tumors, intestinal adhesions, ulcerations, and radiation enteritis) Must not have a current major psychiatric disorder as these may interfere with assessment measures.
- Must not meet DSM-V criteria for moderate to severe substance dependence (other than nicotine or caffeine) within the past 60 days
- Hypersensitivity to riboflavin or any other capsule component.
- Individuals with embedded electronic devices.
- Patients who, in the investigator's opinion, would be unable to comply with study procedures or assessments, or would be unacceptable study candidates (e.g., poses threat to staff).

b. Sources of Materials

- 1) Research material obtained from individual subjects includes questionnaires and interviews with study personnel as well as urine samples. To ensure confidentiality, all subject data will be number coded, and only the investigators will have access to the master lists of codes.

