- 2) The research material will be obtained specifically for research purposes. Written research material obtained will be stored in the Addiction Sciences Division, in an office that is locked when not in use. Any quantitative riboflavin urine samples collected during the study will be stored in the MUSC Clinical Neurobiology Laboratory..

c. Potential Risks

Potential risks associated with capsule ingestion include discomfort in the form of pressure sensations in the esophagus upon ingestion (typically lasting less than 30 seconds), risk of endoscopy pill retention, and a rare risk of capsule aspiration upon attempting to swallow the capsule. There is the risk of breach of confidentiality.

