5.9 Trial Efficacy.

As this is a preliminary investigation, an interim analysis is not planned at the time.

5.10 DSM Plan Administration.

[name] will be responsible for monitoring the study. A DSM report will be filed with the IRB and NIDA on a twice yearly basis, unless greater than expected problems occur or more frequent reporting is requested. The report will include participant characteristics, retention and disposition of study participants, quality assurance issues and reports of AEs, significant/unexpected AEs and serious AEs. We will report outcomes at the end of the trial.

5.11 DSM Board.

As this is a single-site study with a healthy population, a full Data and Safety Monitoring Board is not warranted. The subcontract principal investigator, [name], will have overall responsibility for safety and data monitoring on a day-to-day basis. A detailed Data and Safety Monitoring Plan will be submitted to NIDA prior to study initiation.

5.12 Risk Benefit Ratio.

The assessments and questionnaires are non-invasive and have inherently minimal risks. Potential risks of concern are loss of confidentiality, and adverse events to ID-Cap ingestion. As discussed above, our research team will attempt to minimize these risks. Knowledge gained by the proposed study may be helpful in developing effective treatments for substance use disorders.

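### Group 2 has an abdominal X-ray at End of Study, but the only scheduled pregnancy test is at screening, about five to six weeks earlier

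*Combined protocol and SAP*

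**What the plan says.** **Pregnancy testing.** Under Screening/Assessment: "For female participants, a urine pregnancy test will be completed prior to urine drug screening". The timing follows from the sentence before it: "Urine drug screens will be performed at the screening visit in order to rule out substance abuse". No other pregnancy test appears in the protocol.

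**The X-ray.** Study visits orders it: "For those in Group 2, passage of ID-Caps will be confirmed at this visit via abdominal x-ray". Safety Assessment repeats the order: "An abdominal X-ray will also be completed at study completion to verify passage of the capsules from the gastrointestinal tract". Neither statement carries a condition about pregnancy.

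**Timing.** Study visits places End of Study as follows: "Participants will return to the clinic approximately five weeks (within one week following last dose) after their initial randomization". The same paragraph puts the whole study at roughly six weeks.

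**Safeguards.** The inclusion criteria in section 1a read: "If female and of childbearing potential, must agree to use acceptable methods of birth control for the duration of the trial". The section 1a exclusions cover women who are pregnant, nursing or planning pregnancy during the study. The Subjects paragraph near the start of the protocol also excludes women of childbearing potential who do not use effective contraception.

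**Stated risks.** Section 1c lists esophageal discomfort, "risk of endoscopy pill retention, and a rare risk of capsule aspiration upon attempting to swallow the capsule" and loss of confidentiality. Section 5.12 says: "Potential risks of concern are loss of confidentiality, and adverse events to ID-Cap ingestion". Neither mentions radiation.

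**The concern.** The screening test is in the right place for its own job, which is to enforce the pregnancy exclusion before any capsule is swallowed. It cannot show pregnancy status on the day of the film. A pregnancy that begins after screening, or that was too early for the screening test to detect, could be X-rayed without the participant or the site knowing.

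The film has a genuine safety purpose, because it checks for the capsule retention named in section 1c. It is also the only study procedure that uses ionizing radiation. It is scheduled for every Group 2 participant by protocol rather than prompted by symptoms, and these are healthy volunteers aged 18 to 65. The stake is therefore participant safety. Nothing in the primary comparison depends on it.

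**Working it through.** The plan gives no figure on this point to reproduce. The check is a reading of every contact after screening, followed by a rough size under stated assumptions.

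**1. Is pregnancy checked anywhere between screening and the film?**

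| Contact | What the protocol places there | Pregnancy check |
|---|---|---|
| Screening | Interview, history, physical exam, urine drug screen | Urine test |
| Randomization | Device training, observed dose, dispensing | None |
| Unscheduled Group 2 visits | Urine for riboflavin | None |
| End of Study | Adherence review, equipment return, adverse event question, X-ray (Group 2) | None |

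The adverse event question is given as an open example. It does not name pregnancy, and it is not required to come before the film.

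**2. How long is the gap?**

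- Randomization to film: the last of 30 daily doses falls on day 29 (first dose on day 0) or day 30 (first dispensed dose on day 1). Adding 0 to 7 days gives day 29 to day 37. 29/7 = 4.1 weeks and 37/7 = 5.3 weeks, which agrees with the protocol's figure of about five weeks.
- Screening to film: about five weeks if screening and randomization fall on the same day, and about six weeks if the six-week study duration includes screening. The protocol sets no maximum screening-to-randomization interval, so the gap could be longer.

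**3. How likely is a conception in that gap?**

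From the documents: 20 participants in Group 2 and a gap of five to six weeks. Assumed, because the documents do not say: 5 to 10 women of childbearing potential in Group 2, annual contraceptive failure of 1% to 10%, and half of conceptions recognised by the participant before the film.

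Expected conceptions = women × (weeks/52) × annual failure rate. Chance of at least one = 1 − exp(−expected).

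| Case | Expected conceptions | Chance of at least one | If half are recognised |
|---|---|---|---|
| Low: 5 women, 5 weeks, 1% | 5 × 5/52 × 0.01 = 0.0048 | 0.5% | 0.0024 |
| 10 women, 6 weeks, 1% | 10 × 6/52 × 0.01 = 0.012 | 1.1% | 0.006 |
| 10 women, 6 weeks, 3% | 10 × 6/52 × 0.03 = 0.035 | 3.4% | 0.017 |
| High: 10 women, 6 weeks, 10% | 10 × 6/52 × 0.10 = 0.115 | 10.9% | 0.058 |

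**The case against.** The case on the other side accepts the facts and disputes their weight.

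- **Safeguards.** The Subjects paragraph requires effective contraception, and section 1a excludes women who plan pregnancy. This stands as far as it goes: it makes the high end of the range less plausible, and 1% to 3% failure is a fairer reading. But these criteria prevent pregnancy and do not detect it. The protocol defines neither effective nor acceptable contraception and describes no later check of its use.
- **Soft numbers.** The estimate spans a factor of 24 and rests on assumed inputs. It counts all conceptions in the window. It therefore leaves out pregnancies too early for the screening test, and it includes some too early for a test at End of Study. This stands: the figures give an order of magnitude and do not bound the exposures a repeat test would prevent.
- **Harm not quantified.** The documents give no radiation dose or fetal risk, and none is supplied here. This stands, and the point should not be read as claiming that harm is likely.
- **Unseen material.** Consent pages were removed from the text, the detailed Data and Safety Monitoring Plan is a separate document, and the imaging department may ask about pregnancy as routine. Any of these might cover the gap. The protocol neither requires nor cites such a check, and it gives no instruction for a positive answer.
- **Scope of the risk list.** The section 1c sentence concerns capsule ingestion, so its silence on radiation is weak evidence alone. Section 5.12 is not limited in that way and is silent too.

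**Conclusion.** The concern holds. On the visible text, the last pregnancy test precedes an unconditional abdominal X-ray by about five to six weeks, and nothing in between checks for pregnancy. The people affected are the women of childbearing potential among the 20 in Group 2, a number the documents do not give.

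The risk is low. The chance of at least one conception in the window, across the whole trial, is about 0.5% to 11% over the full assumed range, and about 1% to 3% with 10 women, six weeks and 1% to 3% annual failure. Unrecognised conceptions would be fewer. The conclusion does not depend on these figures: the gap is in the schedule, and it should be closed because the exposure is avoidable and the remedy is cheap. The endpoint and analysis are unaffected. The finding is limited to the visible protocol.

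**What to change.** In Study visits, and again in Safety Assessment, require the following for Group 2 participants of childbearing potential on the day of the film and before exposure:

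1. A urine pregnancy test, and a direct question about possible pregnancy. The question is needed because a urine test can miss a very early pregnancy.
2. If the test is positive, or pregnancy is thought possible, withhold or defer the film. The study physician then decides how capsule passage is followed without radiation.

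Add X-ray exposure to the risks in sections 1c and 5.12. That wording alone would not close the gap.

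The cost is at most 20 urine tests, of a kind the protocol already uses, at a visit participants already attend, plus a few sentences of protocol text. The downside is that a participant whose film is withheld may have no radiographic confirmation that the capsules have passed.

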Hypothesis 1a: The ID-Cap-M system will detect over 95% of medication ingestion events as ascertained by doses of medication recorded by the ID-Cap System that are taken as prescribed (once daily and on time with use of ID-Cap System as instructed) over those scheduled.

Hypothesis 1b: The ID-Cap-M system will have an advantage over the MEMS caps on monitoring and enhancing medication adherence expressed by a proportion of daily medication doses reported by the system to be ingested (ID-Cap System) or accessed (MEMS Caps) as prescribed (defined as within the scheduled administration time) over the study period.

Exploratory Aim 2: To assess the safety of the ID-Cap-M system when used in a healthy population by documenting the frequency and severity of adverse events.

Exploratory Hypothesis 2: Participants randomized to receive the ID-Cap-M system will report similar rates of adverse events as participants randomized to receive standard capsules.

Overview: The primary objective of the clinical trial is to evaluate the acceptability, tolerability, and efficacy of the ID-Cap-M in a healthy population. The primary outcome will be medication compliance as measured by the proportion of days adherent to taking medication over a four week period.

Subjects: 40 participants between the ages of 18 and 65 will be recruited over a 10-month period. Additional inclusion criteria include ability to provide informed consent, functioning at an intellectual

Program Director/Principal Investigator (Last, First, Middle): [name]

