Compensation: Subjects will be compensated \$30 for screening, (\$20 for interview, \$10 for H&P). They will be compensated \$250 for the End of Study visit (\$100 for attendance and \$150 for return of their MEMS 6 TrackCap or ID Cap Reader). If a Group 2 subject did not return for an unscheduled urine sample as requested during the study, they will receive \$50 for attending the EOS visit (versus \$100).

Data Management and Reduction: All paper-based assessments (other than laboratory reports) will be entered into REDCap, a secure, web-based application designed exclusively to support data capture for research studies. REDCap provides an intuitive interface for data entry (with data validation), audit trails for tracking data manipulation, and automated export procedures for data downloading to statistical packages such as SPSS and SAS. Completed assessments will be entered within two weeks after the information has been collected from the subject. Quarterly database management and data integrity audits will be conducted and reports submitted.

Statistical Methods: Univariate descriptive statistics and frequency distributions will be calculated for all variables. Departures from distributional assumptions for the proposed parametric methods will be identified and appropriate transformations of the data will be applied or alternative procedures (semi/non parametric methods) will be employed. Values for demographic, clinical, and other prognostic variables will be compared for imbalance across treatment groups. ***Aim 1:*** The hypothesis

Program Director/Principal Investigator (Last, First, Middle): [name]

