that the ID-Cap-M will improve compliance will be tested by comparing the number of medication adherent days (defined as ingestion of dose of medication within one hour of scheduled time) in the group receiving the ID-Cap-M with the group using a MEMS 6 TrackCap. The primary analysis of the difference in the number of adherent days will be done using a two group ANOVA model. Additional model analysis will be conducted assuming a binary pattern of responses on each day and fit into a Generalized Linear Model using a Generalized Estimating Equations (GEE) framework. **Exploratory Aim 2:** To test the safety and tolerability of ingestion of the ID-Cap-M versus standard capsules, the number of adverse event reported in the 20 subjects taking the ID-Cap will be compared to the number of events in the 20 subjects assigned to standard capsules. Analysis will be performed using a Pearson Chi-Square test statistic.

Other Statistical Considerations: The primary method of analysis will be through the use of the intent to treat sample where missing compliance data will be deemed non-adherent. However, other methods of missing data analysis will be employed and a sensitivity analysis of the various methods will be presented.

Sample Size Justification: The proposed study intends to evaluate the feasibility of inclusion of ID-Caps to monitor compliance in medication trials involving substance abusing subjects. The current study is a 30-day efficacy evaluation of the ID-Cap-M versus MEMS 6 TrackCap. **Aim 1:** With 20 subjects receiving the active ID-Caps and 20 receiving MEMS 6 TrackCap, we will have 80% power with a two sided $\alpha=0.05$ to detect an effect size of 0.95 (Cohen's *d*), which is equivalent to a difference of 0.95 adherent days between the two study groups for each unit in the standard deviation (example: with a SD of 10 days, we will be able to detect a difference of 9.5 days between groups)..

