An Adverse Event (AE) is defined as any untoward medical occurrence in a study subject administered a pharmaceutical product that does not necessarily have a causal relationship with this treatment (ICH GCP). Any unwanted change, physically, psychologically or behaviorally, that occurs in a study participant during the course of the trial is an adverse event. A Serious Adverse Event (SAE) is defined as an adverse event that has one of the following outcomes:

- Results in death,
- Is life-threatening,
- Requires inpatient hospitalization or prolongation of existing hospitalization,

Program Director/Principal Investigator (Last, First, Middle): [name]

- Results in persistent or significant disability/incapacity,
- Is a congenital anomaly/birth defect OR
- Requires intervention to prevent one of the above outcomes.

5.7 Documentation and Reporting. AEs/SAEs are documented and reported as per protocol and IRB requirements. Research staff will identify adverse events and obtain all available information to assess severity, seriousness, study relatedness, expectedness, outcome and the need for change or discontinuation in the study intervention. Adverse events are generally documented on AE Logs and AE Case Report Forms (CRFs). Additional relevant AE information if available should be documented in a progress note in the research record as appropriate to allow monitoring and evaluating of the AE. If the AE meets the definition for serious, appropriate SAE protocol specific reporting forms are completed and disseminated to the appropriate persons and within the designated timeframes as indicated above. For each AE/SAE recorded, the research staff will follow the AE/SAE until resolution, stabilization or until the participant is no longer in the study as stated in the protocol. When a reportable SAE is identified, the research staff will notify the MUSC Institutional Review Board (IRB) within 24 hours and complete the AE report form in conjunction with the PI. The MUSC IRB meets monthly and is located at [name]. Communication with the IRB is through email, memos, official IRB forms, and online reporting. A report will also be sent to the NIH program officer assigned to the project.

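### Exploratory Aim 2 applies a Pearson chi-square to numbers of adverse events without setting the participant as the unit of analysis

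*Combined protocol and SAP*

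**What the plan says.** Under Statistical Methods, Exploratory Aim 2, the comparison is set out in two sentences. The first says that "the number of adverse event reported in the 20 subjects taking the ID-Cap will be compared to the number of events in the 20 subjects" in the control arm. The second adds: "Analysis will be performed using a Pearson Chi-Square test statistic". No table layout is given, nor any rule for a subject with more than one event.

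Other sections bear on how many events a subject can contribute:

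- Safety Assessment has the clinician ask at the End of Study visit: "Have you had any problems or side effects since we saw you last (such as flu, headache, nausea, or other problems".
- Section 5.6 defines the term broadly: "Any unwanted change, physically, psychologically or behaviorally, that occurs in a study participant during the course of the trial is an adverse event".
- Section 5.7 handles events one by one: "For each AE/SAE recorded, the research staff will follow the AE/SAE until resolution" or another end point.

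The aim is to assess safety "by documenting the frequency and severity of adverse events". Exploratory Hypothesis 2 is that ID-Cap-M participants "will report similar rates of adverse events as participants randomized to receive standard capsules". Statistical Methods also promises: "Univariate descriptive statistics and frequency distributions will be calculated for all variables". No interval, margin or power for adverse events appears anywhere.

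**The concern.** A Pearson chi-square assumes that the units counted in its cells are independent. Twenty randomized subjects per arm meet that condition. Adverse events need not, because a subject who reports headache may also be more likely to report nausea. If events are the counting unit, a few subjects with many complaints can drive the result, and the p-value overstates the evidence for a difference.

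Because the unit is not stated, two analysts could follow the same text and reach opposite answers. Suppose four ID-Cap subjects have three events each and four control subjects have one each. On event totals the comparison is 12 against 4; on subjects it is 4/20 against 4/20.

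A secondary matter is that the hypothesis predicts similarity, while the only planned inference is a test for a difference. With 20 per arm, a non-significant result would not by itself support similar rates. The safety comparison will be read, since Design Considerations makes the move to drug-dependent populations follow from establishing safety and efficacy here.

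**Working it through.** **Inputs.** From the plan: 20 subjects per arm, and events as the named quantity. The plan gives no figure for Aim 2 to reproduce. Assumed: mean events per subject m of 0.1, 0.2, 0.5 or 1, equal in both arms. Counts are either Poisson or gamma-Poisson with shape k of 1 or 0.5, so that variance/mean = 1 + m/k. Tests are at the nominal 5% level. That level is also assumed, because the plan states alpha for Aim 1 only.

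**The worked example.** For arm totals a and b with equal numbers of subjects, the chi-square on event totals is (a − b)²/(a + b). With 12 and 4 events, (12 − 4)²/16 = 4.0, p = 0.046. On subjects, 4/20 against 4/20 gives p = 1.0.

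**False-positive rate on event totals.** The arm total is Poisson(20m), or negative binomial with mean 20m and shape 20k. The probability that (a − b)²/(a + b) exceeds 3.84 was summed exactly over all pairs of totals:

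| Mean per subject | Poisson | Shape 1 | Shape 0.5 |
|---|---|---|---|
| 0.1 | 4.13% | 4.91% | 5.71% |
| 0.2 | 4.47% | 6.49% | 8.56% |
| 0.5 | 5.19% | 10.97% | 16.34% |
| 1 | 4.94% | 16.35% | 25.41% |

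**False-positive rate on subjects.** The probability of at least one event is 1 − exp(−m) for Poisson counts and 1 − (k/(k + m))^k otherwise. At m = 1, k = 1 it is 1 − 1/2 = 0.50. Enumerating the two binomials with n = 20 over the same 12 settings gives 3.3% to 5.3% for the Pearson chi-square and 0.9% to 2.5% for Fisher's exact test. A pooled t-test on per-subject counts (200,000 simulated trials per setting) gives 3.1% to 5.0%.

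**Effect of an automatic Fisher switch.** With equal arms, an expected cell falls below 5 whenever fewer than 10 of the 40 subjects have an event (10/2 = 5). At means of 0.1 to 0.2 with equal rates this happens in 82% to 99.8% of trials. Power for a doubled rate would fall as follows:

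| Mean, doubled | Subject-level Pearson | With Fisher switch |
|---|---|---|
| 0.1 to 0.2 | 9% to 12% | 4% to 6% |
| 0.2 to 0.4 | 12% to 19% | 9% to 17% |

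**Width of the interval for similarity.** For identical observed proportions p with Wilson limits l and u, the Newcombe half-width is √[(p − l)² + (u − p)²].

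- 0/20 each: l = 0, u = 0.161; half-width 0.161.
- 1/20 each: l = 0.009, u = 0.236; half-width √(0.041² + 0.186²) = 0.191.
- 4/20 each: l = 0.081, u = 0.416; half-width √(0.119² + 0.216²) = 0.247.

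**The case against.** The strongest reply is that a table of subjects was meant. The sentence gives 20 subjects for each arm, the hypothesis is about participants, and a Pearson chi-square with fixed group sizes is commonly a table of subjects by arm, which is valid. The event-total statistic used above appears nowhere in the plan. This stands as far as it goes: the supportable claim is that the unit is not stated, and inflation follows under only one way of resolving that. It does not remove the point, because the text names events in both arms and nothing reduces them to one per subject. A table of events over 20 would also break down if an arm had more than 20 events.

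Second, the inflation depends on rates and dispersion that the documents do not give. This also stands. Poisson counts produce no problem, and even with clustering (mean 0.1, shape 1) the rate is 4.9%. The 16% to 25% range needs about one event per subject and marked heterogeneity, and nothing in the documents points to that for healthy adults taking a riboflavin capsule.

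Third, other clauses might seem to cover the gap. They do not. The allowance for alternative procedures concerns distributional assumptions of parametric methods and does not set the unit. GEE is named only for daily adherence.

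Fourth, a reader might infer that a non-significant test will be reported as proof of similarity. The documents do not say so. Aim 2 has no alpha, margin or decision rule, and is to be met by documenting frequency and severity. The interval is therefore a secondary recommendation.

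**Conclusion.** The point holds as an unstated unit of analysis, with a literal reading that can treat several events from one subject as independent. Under that reading the false-positive rate is about 4% to 5% if counts are Poisson. With gamma shape 1 to 0.5 it is 5% to 9% at means of 0.1 to 0.2, 11% to 16% at 0.5 and 16% to 25% at 1. All of this rests on assumed rates and dispersion.

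A reader might go further and conclude that the planned safety test is invalid, or that its error rate will reach 25%. The documents do not support that: the intended table may be one of subjects, and the inflation is absent or small when events are rare or unclustered.

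Severity is minor. The consequence is limited to how the exploratory safety comparison is analysed and reported. The primary analysis, the sample size and the handling of individual adverse events are unaffected.

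**What to change.** Replace the Aim 2 analysis text, before adverse event data are compared between arms, with:

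*The number of participants with at least one adverse event, each counted once, will be compared between arms by Pearson chi-square, and the risk difference will be reported with a Newcombe 95% confidence interval. Event totals by type and severity will be listed descriptively.*

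Base any statement about similar rates on the interval. Do not add an automatic switch to Fisher's exact test: the subject-level Pearson test already holds its level in the settings examined, and the switch would roughly halve power when events are rarest.

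The change is to wording only and needs no new data, visits or subjects. Its statistical cost is lost sensitivity to repeated events when these are frequent. For a rate doubled from mean 1 to 2 with shape 1, power is 18% for the subject-level chi-square against 33% for a t-test on per-subject counts; from 0.5 to 1 it is 18% against 24%. At means of 0.1 and 0.2, doubled, the two are alike (9% to 19% against 8% to 19%). If repeated events matter to the sponsor, a per-subject comparison of mean counts with its interval can be prespecified as a supplement.
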